17. Describe the plan for protecting research data from improper use or disclosure. The participant will be assigned a 4-digit unique identifying number for this study. This 4-digit identification number will not be related to the last 4 digits of his social security number or a 4-digit number generated by scrambling his social security number. The link between the 4-digit coded identification number and the participant's name and social security number will be stored on paper in a locked cabinet in room # 228 B or in a locked cabinet in the [name] locked room and also backed up electronically in the password protected VA online drives. Data on paper will be stored in locked cabinets and locked desk drawers in the MIRECC office space in room number 228 B. Electronic data will either be stored on the password protected online drive of the CMCVAMC. The actigraphic data will be stored on the research assistant's password protected desktop, the principal investigators desktop, and backed up on a compact disc as recommended by the manufacturer and as is being done in our current CBT-I pilot study. All the discs will be stored in the principal investigators locked office space with restricted access (room # TBA), in a locked cabinet. CMCVAMC Information Security Officer and Privacy Officer will be notified within one hour of the improper use or disclosure, as well as the IRB, Associate Chief of Staff for Research (ACOS/R) and Research Compliance Officer.

17.1. The Investigator must notify the Information Security Officer, Privacy Officer, IRB, Associate Chief of Staff for Research and Research Compliance Officer within one hour of the improper use or disclosure.

18. Is there a plan to apply for a Certificate of Confidentiality? YES NO N/A
 18.1. If yes, provide a copy of the certificate with this application or to the IRB Office as soon as received.

19. **Record Retention:**

- 19.1. The required records, including the investigator's research records, must be retained until disposition instructions are approved by the National Archives and Records Administration and are published in VHA's Records Control Schedule (RCS 10-1). VHA Handbook 1200.05 §26.h
- 19.2. Until a schedule for local research records is published, ALL records including identifiers must be retained." ORO/ORD Guidance on Informed Consent Form Modifications Addressing VA Record Retention Requirements (July 23, 2009)

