 Surveys/Questionnaires	 Interviews	 Audio Taping
 Behavioral Observations	 Chart Reviews	 Video Taping
 Focus Groups	 Randomization	 Double-Blind
 Control Group	 Placebo	 Withhold/Delay Treatment
 Specimen Collection	 Deception	 Telephone Survey
 Other (Describe)		

Eight Session CBT-I: General Protocol. Cognitive Behavioral therapy is conducted in 8 sessions during which subjects meet individually with the study clinician. Session 1 serves as an orientation. No active treatment is delivered at this time. Sessions 2 & 3 are used to deliver the three main components of the intervention which are Sleep Restriction (SRT)^{42,43}, Stimulus Control⁴⁴⁻⁴⁶, and Sleep Hygiene⁴⁷⁻⁴⁹. All but two of the remaining sessions are dedicated to the titration of total sleep time and to ensuring patient adherence. One session (session 5) entails the delivery of a specific form of cognitive therapy. The cognitive element targeted in this session is modeled on Barlow's approach to the cognitive restructuring of catastrophic thinking as it occurs in insomnia with panic disorder. This approach was adapted to address the catastrophic thinking as it occurs in insomnia in relation to the consequences of poor sleep. The final session (session 8) is used to engage in a relapse-prevention didactic, i.e., to review first, how insomnia becomes chronic and second, the strategies that are likely to abort an extended episode of insomnia. The specific details for each of the above interventions (e.g., titration rules, stimulus control rules, etc.) and itineraries for each of the individual sessions are detailed in the Penn treatment manual (published by Springer in 2005 [hardback] and re-printed in 2008 [paperback])⁵⁰.

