Quasi-Desensitization Placebo Therapy (QDT). This form of placebo therapy has been commonly used in prior studies investigating behavioral interventions for insomnia^{9,13,51,52}. The therapist presents the QDT as a means to eliminate "conditioned arousal," occurring after nocturnal arousal using 8 sessions on a weekly basis. The therapist initially helps the subject to develop a chronological 12-item hierarchy of commonly practiced activities on awakening at night, like opening eyes and clock watching. As a next step, the subject develops 6 imaginal scenes of himself/herself engaged in neutral activities like reading a newspaper. The therapist then helps the subject pair the neutral scenes with the items from the 12-item hierarchy, which is then practiced by the subject ≥ 2 hours before bedtime.

- 2.2. Describe how randomization or other treatment assignment will be made. **Subjects will be block randomized using a computer generated randomizing sequence.** Participants are randomly assigned to the CBT-I group, or the QDT group. The study biostatistician will create randomization sequences by family history of alcoholism (separate sequences) using a pseudo-random number generator with block sizes of 4. Two boxes of sequentially numbered, sealed, opaque envelopes will be prepared using the randomization sequences and labeled "Family History" and "No Family History". At the time of randomization, the first envelope, in sequential order, is pulled from the appropriate box and opened to reveal the group assignment. All the staff conducting assessments will be blinded to the allocation of treatment arm with the exception of Dr.

[name], the BSM treatment provider, [name] the person overseeing treatment allocation, and [name], the monitor for BSM treatment for the study.

- 2.3. For retrospective research studies, provide the "look-back" period. (e.g., December 1, 1999 through December 31, 2008.) **N/A.**

3. **Study Duration**

- 3.1. Provide the estimated length of time to enroll all subjects and complete the study. **Five years.**
- 3.2. Explain the expected duration of subject participation including any follow-up. **Eight months.**
- 3.3. Specify the projected date of completion of the proposed study. **Dec. 2018.**

4. **Drug Information.** Not Applicable.

5. **Investigational Device.** Not Applicable.

M. **Does this project involve international research?** YES NO

N. **Study Procedure.** Please see Table 1 for all the study-related procedures.

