
early phases of the study, using laboratory data, inclusion and exclusion criteria, and other person-specific information). Personnel involved will include the following: Principal investigator, study coordinator, behavioral sleep medicine practitioners associated with this study.

- 9.5.6. Include the breakdown of each individual's responsibilities:
 - 9.5.6.1. **Principal Investigator.** He may fulfill any of the roles required for the study, including, answering questions for prospective participants, informed consent procedure for participation for assessment for study entry, baseline assessments, assessments as part of the study visits, conducting the cognitive behavioral therapy sessions, scheduling the participant sessions, post-study assessments, conducting the urine drug screens, drawing blood and preparing the blood sample for storage in the freezer, coordinating clinical care with other providers.
 - 9.5.6.2. **Co-Principal Investigator, N/A**
 - 9.5.6.3. **Research Coordinator.** S/he will be involved in answering questions for prospective participants, informed consent procedure for participation for assessment for study entry, baseline assessments, assessments as part of the study visits including the urine drug screen test at baseline, drawing blood samples (after completion of the requisite training), scheduling the participant sessions, post-study assessments.
 - 9.5.6.4. **Additional research staff by title.** a. Phlebotomy – either [name] or a designated staff certified and IRB-approved to draw blood will conduct the blood draws and prepare the samples for the storage in the designated R & D freezer space; b. Certified Behavioral Sleep Medicine Provider: s/he will conduct the CBT-I and the QDT sessions for the participants; the Principal Investigator, [name] will conduct CBT-I or QDT as a backup provider.
- 9.6. Will informed consent be obtained from potential subjects prior to determining eligibility?
 YES NO N/A
 - 9.6.1. If no, provide justification and a HIPAA Waiver of Individual Authorization for Disclosure of Protected Health Information.
- 9.7. **Define when a subject is enrolled into the study, e.g. after the subject signs the informed consent or after randomized to treatment.** After he is randomized into a treatment arm.
- 9.8. Describe:

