1. **Describe how and when a subject may withdrawal from the study.** Once the subject completes the first session of the CBT-I, he will not be dropped from the study, unless they specifically request that they not be contacted, or the subject cannot be located for assessment by the 8-week follow-up. The subject may voluntarily withdraw from the study at any point in time. Subjects who are discontinued from the cognitive behavioral therapy intervention will continue to be followed in the study until the completion of the 8 weeks of intervention and the post-study follow-up at 3 and 6 months. The reason the subject is discontinued from the study and any referrals that are made are documented in the appropriate section of the subject's casebooks.
2. **Provide procedures for the orderly termination of participation by the participant and if any consequences would result from early withdrawal from the study.** The subject may be terminated from the research study by the investigator, without regard to his/her consent, under certain conditions. These conditions may include, if s/he does not comply with the recommendations of the research staff, including compliance with study related procedures on ≥3 consecutive office appointments; s/he reports ideas of harm to self or to anybody else with any intent and/or a plan. S/he will additionally be referred to the outpatient treatment program at the Addiction Recovery Unit of the CMCVAMC. Alternatively patient will be withdrawn from the study on successful completion of their study participation.

Subjects will be discontinued/withdrawn from the study if any of the following events occur:

- Any condition which the study psychiatrist finds CBT-I to be a hazard to the subject (i.e. patient seen to be agitated, onset of increasing paranoia, inability to follow through with recommendations and/or homework)
- Participant screens positive at baseline for moderate to severe obstructive sleep apnea (as seen baseline screening portable sleep monitor data), and is currently on not treatment for the obstructive sleep apnea
- Relapse to sustained heavy drinking during treatment as quantified at ≥ 5 standard drinks for men and ≥ 4 standard drinks for women less than 70 years of age, or a total of 14 drinks/ week in men and 7 drinks per week in women for ≥4 days a week and >1 week;

- Development of an inter-current medical illness or condition that requires a new hospital admission

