
Specific Aims 1-3: The analysis for the specific aims 1-3 is based upon the intent-to-treat principle; all randomized participants will be included in the analysis regardless of whether they drop out of the intervention or study. The analysis will involve the comparison of the insomnia severity (Aim 1), abstinence from drinking (Aim 2), and quality of life (Aim 3) across the intervention groups in order to allow for different trajectories of the outcome measures and to afford flexibility in making contrasts within participants over time and across participants while simultaneously controlling for potential confounding factors, we propose the participant-specific or *mixed effects* linear

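### The retention commitment names only CBT-I, starts at its first session and lapses for anyone not located by week 8; it should be one rule for both arms from randomisation

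*Combined protocol and SAP*

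**What the plan says.** Section S.1 (Withdrawal/Early Withdrawal) sets the retention commitment: "Once the subject completes the first session of the CBT-I, he will not be dropped from the study". It has two exceptions. One is a request not to be contacted. The other is that "the subject cannot be located for assessment by the 8-week follow-up". Later in the same paragraph, "Subjects who are discontinued from the cognitive behavioral therapy intervention will continue to be followed in the study", through the 8 weeks and the 3- and 6-month visits. Neither sentence mentions QDT.

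Section S.2 adds investigator termination and a list headed "Subjects will be discontinued/withdrawn from the study if any of the following events occur". The list is not limited to one arm, and it does not say whether outcome assessment continues afterwards.

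Other relevant places are:
- Section L.2.1: QDT is also delivered "using 8 sessions on a weekly basis". Of CBT-I it says: "Session 1 serves as an orientation. No active treatment is delivered at this time".
- Section Q.9.7 defines when a subject counts as enrolled: "After he is randomized into a treatment arm".
- Section V.4.2: the treatment effects are the between-arm differences in change from baseline at 3 and 6 months. Under intention to treat, "all randomized participants will be included in the analysis regardless of whether they drop out of the intervention or study".
- Section N.2.1.1: randomised Veterans are treated for 8 weeks and seen at 3 and 6 months, with phone or mail assessment for those who cannot attend.

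**The concern.** The text leaves three gaps.

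- **Arm.** Both operative sentences in S.1 name the experimental therapy and neither names the control. Staff working from this text have an explicit duty to keep following one arm and none for the other.
- **Start.** The commitment begins at a session that delivers no active treatment, although enrolment is at randomisation. Someone who leaves between the two falls outside it. With baseline data alone, that person adds almost nothing to a change-from-baseline contrast, even though formally in the analysis set.
- **Week 8.** A subject not located by then may be dropped, yet the contrasts that define the treatment effects come later.

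Section Q.7.1 says that many of these Veterans are unemployed and live in shelters, so being unreachable for a time at week 8 is plausible and need not be permanent. Loss of contact could also track relapse, and percentage of days abstinent is the primary alcohol outcome. Missingness would then be informative. The plan imputes only if missingness shows significant associations, and standard imputation does not remove bias that depends on unobserved relapse.

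**Working it through.** **The plan's own figure.** Section V.4.1 gives 43 per group, 30 after 30% attrition, and 80% power for 0.50 SD at 6 months with intra-class correlation (ICC) 0.3, up to 10 follow-up measures and two-sided alpha 0.025. (The note to the detectable-difference table says 0.05, which is a separate matter. At 0.05 the power would be 88.9%, so the 80% fits 0.025.)

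- Attrition: 43 × 0.70 = 30.1, and 30 / 0.70 = 42.9, so 43. Reproduced.
- Variance factor for the mean of m = 10 measures: (1 + 9 × 0.3) / 10 = 0.37.
- Required n per arm: 2 × (2.241 + 0.842)² × 0.37 / 0.50² = 28.1, so 29. Inflated: 29 / 0.70 = 41.4, so 42, against 43 stated.
- Power at 30 per arm: SE = √(2/30 × 0.37) = 0.157, and Φ(0.50 / 0.157 − 2.241) = 82.7%. With 9 or 8 measures it is 81.8% or 80.8%, close to the stated 80%.

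The 30% is one rate for both arms and all causes. Nothing in the documents says how much of it comes from subjects not located at week 8, or how it splits by arm. The effect of the S.1 wording therefore cannot be derived. The figures below rest on assumed rates.

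**Unequal loss.** Same formula with SE = √((1/n₁ + 1/n₂) × 0.37), n rounded down from 43:

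| Assumed loss, arm 1 / arm 2 | n | Power at 0.50 SD | Detectable at 80% power |
|---|---|---|---|
| 30% / 30% | 30 / 30 | 82.7% | 0.48 SD |
| 30% / 35% | 30 / 27 | 80.4% | 0.50 SD |
| 30% / 40% | 30 / 25 | 78.6% | 0.51 SD |
| 30% / 50% | 30 / 21 | 74.1% | 0.53 SD |
| 40% / 40% | 25 / 25 | 74.7% | 0.53 SD |

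**Bias from unequal loss.** If lost subjects are D SD worse than retained ones in both arms, a complete-case difference shifts by (loss₂ − loss₁) × D. For 30% / 40% and D = 0.5, that is 0.10 × 0.5 = 0.05 SD, or 0.05 × 3.809 = 0.19 ISI points. For 30% / 50% and D = 1, it is 0.20 SD, or 0.76 points. The plan's detectable ISI difference is 1.90 points.

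**Recovery.** If one third to one half of the 13 lost per arm (43 − 30) could be reached later, n would rise to about 34–36. The standard error would fall by 1 − √(30/34) = 6% to 1 − √(30/36) = 9%. This is optimistic. It treats all 13 as reachable, and in the planned mixed model dropouts with earlier measures already contribute.

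**Passages side by side.** Enrolment is at randomisation and the commitment starts later. Therapy has 8 sessions in both arms, and the commitment names one. The tested contrasts are at 3 and 6 months, and the exception applies at week 8. S.1 follows subjects who stop therapy, while S.2 withdraws subjects from the study for listed events.

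**The case against.** The best defence is that this is loose drafting. The protocol uses CBT-I loosely elsewhere: the withdrawal list in S.2, which applies to all subjects, speaks of CBT-I being a hazard. Several provisions are neutral between arms. Section N.2.1.1 plans 3- and 6-month visits for everyone randomised, follow-up payments in section R do not depend on arm, and section T.1.3 allows a subject withdrawn for risk to be monitored to the end of the study. Assessors are blinded, with listed exceptions, which limits deliberate differences in effort. All of this stands, and it makes a planned difference in retention unlikely. It does not supply the missing commitment for QDT.

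A reader might go further and infer three things that the documents do not support:
- *That QDT participants are dropped or followed less.* The text is silent on QDT; it says nothing adverse.
- *That only first-session completers are protected and anyone missed at week 8 is dropped.* The week-8 clause is an exception to a promise and covers people who cannot be found. The sentence on follow-up after stopping therapy carries no first-session condition.
- *That the rule breaks intention to treat.* Section V.4.2 expressly keeps study dropouts, 30% loss is budgeted, the mixed model accommodates dropout, and multiple imputation is planned conditionally. The tension is with how completely outcomes are collected.

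**Conclusion.** The point holds as a gap in the retention rule. Read literally, S.1 permits follow-up to differ by arm, leaves the time between randomisation and session 1 uncovered, and allows collection to stop before the 3- and 6-month outcomes for people who might be reached later. Conditional imputation does not replace outcomes that were never sought.

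Its size is unknown. Under the assumed rates above, power at 0.50 SD runs from 82.7% down to 74.1%, and the illustrative complete-case bias reaches 0.76 ISI points only with a 20-point gap in loss and a 1 SD difference between lost and retained subjects. These figures show what could be at stake and do not estimate what the wording would cause. The change is worth making because it is specific and cheap.

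**What to change.** In S.1, make randomisation the trigger in place of the first CBT-I session, and refer to the assigned intervention where the follow-up sentence names cognitive behavioural therapy. Suggested text:

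*From randomisation onward, in both arms, outcome follow-up continues unless the participant withdraws consent for contact. Anyone not located or missed at week 8 is still approached at 3 and 6 months, by phone or mail if needed.*

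Reconcile the termination and withdrawal provisions in S.2 with this statement and with section V.4.2. For each event, say whether it stops the intervention, outcome assessment or both. The clinical criteria themselves need not change for this purpose.

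The cost is a protocol wording amendment and some further contact attempts. Phone and mail assessment and payment for the follow-up visits are already in the plan.

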 - c. Relapse to Alcohol: there is a possibility that the transient "side effects" of CBT-I may lead some individuals to resort to occasional alcohol use and that such behavior may also lead to relapse (heavy drinking);
 - d. Use of Other Drugs: there is a possibility that the transient "side effects" of CBT-I may lead some individuals to start using other drugs while taking part in the study-related procedures;
 - e. Suicidal/Homicidal Ideation. While there is no evidence that CBT-I increases suicidal or homicidal ideation, it is a possible consequence of the transient sleep deprivation that occurs with CBT-I. That is, sleep deprivation may lead to decreased inhibition in the frontal brain areas, which may, in turn, lead to a failure to inhibit or cope with such thoughts, especially in vulnerable populations like those who suffer from alcoholism.
 - 1.1.3. Social. A decreased interest in affiliating with other people because of persisting insomnia or a transient increase in the insomnia secondary to the sleep restriction associated with the CBT-I.
 - 1.1.4. Economic. Time spent participating in the study may interfere with the subject's ability to seek employment or participate at his job.

- 1.1.5. Monetary. May be secondary to loss of time spent in participating in the study.
 - 1.1.6. Legal. An increase in the drowsiness may lead to potential risk of a motor vehicle accident.
 - 1.1.7. Loss of confidentiality a. there is a possibility that the subject's identifying data and/or study information may be viewed by non-study personnel.
 - 1.1.8. Assess the likelihood and seriousness of such risks. Although the risks associated with drowsy driving are serious, the likelihood of this risk is low. The likelihood of the other risks are variable, between a low to a moderate level, and specific to the Veteran's individual situation.
 - 1.1.9. Other. N/A
- 1.2. Specify what steps will be taken to minimize these risks.
- a. Portable Sleep Apnea Monitoring: While the use of nasal cannulas and sensors on the stomach and abdomen are required for this screening, subjects that experience discomfort during orientation will be provided (where possible) the opportunity to select from different types of cannulas and sensors .

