 - e. Confidentiality: During the participation in this study, the patient will be assigned a 4-digit unique identification number. This number will not be derived from PHI of any sort (e.g., DOB, SSN, etc.) and will simply represent the study and the subject's recruitment number (e.g., 1001). Study numbers will be linked to subject identifiers in one spreadsheet that will be stored on the PI's password-protected VA online drive. These efforts make it very unlikely that the subject's identifying data and/or study

information may be viewed by non-study personnel. The data will now be captured and stored within the VA Redcap and stored in the secured VA servers.

- f. Relapse to the Drinking. All drinking behavior will be monitored. Monitoring will be based upon self-report items on the daily sleep diaries and clinical interviews by the principal investigator during the outpatient visits. These variables will be monitored for both research and clinical purposes. The research purpose is to determine how alcohol use varies with treatment for insomnia. The clinical purpose is to be able to determine if there has been a resumption of heavy drinking (four standard alcoholic drinks on any day or ≥ 14 drinks a week). If there is a resumption of sustained heavy drinking and this sustained heavy drinking places the subject at risk of medical, psychological or physical harm, then he will be withdrawn from the study, and a referral to the ARU or the inpatient unit, as deemed necessary for further treatment, will be offered to the participant
- g. Use of Other Street Drugs. Patients will be evaluated for the use of other street drugs through structured assessment instruments. Further, if there is a history of regular drug use, the subject will be regularly monitored with standard urine tests (note: this will be a condition for admittance into the study). If regular drug use is detected, the subject will be withdrawn from the study, and a referral to the ARU for further treatment will be offered to the participant.

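### Section S, item 1 keeps participants in follow-up while item 2 withdraws sustained heavy drinkers, and nothing says whether Aim 2 drinking data are still collected after that withdrawal

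*Combined protocol and SAP*

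**What the plan says.** All references are to the combined protocol and SAP.

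- **Section S, item 1.** Once the first CBT-I session is completed, "he will not be dropped from the study, unless they specifically request that they not be contacted, or the subject cannot be located" by the 8-week assessment. Voluntary withdrawal is allowed at any time. "Subjects who are discontinued from the cognitive behavioral therapy intervention will continue to be followed in the study" through week 8 and to the 3- and 6-month visits. Drinking is not an exception. The text names only CBT-I and does not state the rule for QDT participants.
- **Section S, item 2.** "Subjects will be discontinued/withdrawn from the study if any of the following events occur". One event begins "Relapse to sustained heavy drinking during treatment as quantified at" and ends with "7 drinks per week in women for ≥4 days a week and >1 week". The wording is mandatory and refers to the study, not to the intervention.
- **Section T, item 1.2(f).** Drinking is monitored partly for research: "The research purpose is to determine how alcohol use varies with treatment for insomnia". When sustained heavy drinking "places the subject at risk of medical, psychological or physical harm, then he will be withdrawn from the study". This condition is narrower than item 2 because it adds risk of harm. It is not limited to the treatment period, and it defines heavy drinking differently.
- **Section T, item 1.3.** In extreme situations the investigator may withdraw a subject and monitor him to the end of the study.
- **Section V, item 4.2.** All randomized participants are analysed by intention to treat, using a mixed model. Multiple imputation is added if missingness is associated with the model variables.

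**The concern.** Percentage days abstinent from the TLFB is the primary alcohol outcome (Section J) and the endpoint of Aim 2 (Section I). A rule that removes people for sustained heavy drinking, if it also ends assessment, stops measuring that outcome in the people for whom it is worst.

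The protocol gives reasons to think that relapse may differ between arms. Aim 2 predicts less recidivism with CBT-I. Section T, item 1.1.2(c) warns that transient effects of CBT-I "may lead some individuals to resort to occasional alcohol use and that such behavior may also lead to relapse (heavy drinking". In either direction, losing relapsers from measurement makes the arms look more alike, so a benefit or a harm could be understated. Section V, item 4.2 itself treats complete data as necessary for unbiased estimates.

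**Working it through.** **1. The plan's own yardstick.** Inputs from Section V, item 4.1: SD for abstinent days 15.96, effect size 0.50 SD, 30% attrition, 43 per group.
- Detectable difference: 0.50 × 15.96 = 7.98 points, as stated.
- Completers: 43 × 0.70 = 30.1, matching the stated 30 per group.

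The 7.98 points serve below only as a scale for the loss.

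**2. The rules applied to one case.** Take a CBT-I participant who meets the drinking criterion in week 4.
- Section S, item 1: retained, and followed to 6 months if taken off CBT-I.
- Section S, item 2: must be withdrawn from the study.
- Section T, item 1.2(f): withdrawn only if the drinking also creates a risk of harm.

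These cannot all be obeyed. For a QDT participant, item 1 gives no retention rule.

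**3. Whether another section settles it.**
- Section T, item 1.3 is discretionary, and the monitoring it mentions is not defined as outcome assessment.
- Section V, item 3.3 keeps following participants with new drug abuse or dependence, but Section T, item 1.2(g) withdraws them for regular drug use. The same conflict recurs there.
- The end of Section S, item 2 makes restarting study procedures depend on still meeting eligibility criteria. That suggests withdrawal does stop procedures.
- Intention to treat says who is analysed. It cannot supply days that were never collected.

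No section says that the TLFB continues after withdrawal under Section S, item 2 or Section T, item 1.2(f).

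**4. What the analysis could recover.** The mixed model and the imputation both rely on data being missing at random. Withdrawal on recorded drinking does not automatically violate that. But if nearly all relapsers are withdrawn, there are few post-relapse observations from which to predict the missing ones.

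**5. Size, on assumed values.** Let p_Q and p_C be the proportions withdrawn after relapse in QDT and CBT-I, and let s be the 6-month shortfall in percentage days abstinent per relapser. If nothing after relapse is recovered:

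loss in the Aim 2 difference ≈ (p_Q − p_C) × s

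- Assumed abstinence without relapse: 95% (not in the documents).
- Abstinence in relapse: at most 3/7 = 42.9%, if the four-day count qualifies the whole item 2 trigger.
- No relapser remits: s = 95 − 42.9 = 52.1, about 52.
- Half remit: s = 52.1 / 2, about 26.

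| p_Q − p_C | s = 26 | s = 52 |
|---|---|---|
| 0 | 0 | 0 |
| 0.05 | 1.3 | 2.6 |
| 0.10 | 2.6 | 5.2 |

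A difference of 0.10 is about four participants (0.10 × 43 = 4.3). Against 7.98 points, 2.6 is 33% (2.6 / 7.98) and 5.2 is 65% (5.2 / 7.98).

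**The case against.** The strongest reply is that most of the text leans towards continued follow-up. Section S, item 1 follows people taken off the intervention, and its closing sentence appears to call the same event discontinuation from the study, so the terms are used loosely. The first event in item 2 concerns CBT-I being hazardous, which is a reason to stop therapy. Section T, item 1.3 pairs withdrawal with monitoring, Section V, item 3.3 continues follow-up, and the analysis is by intention to treat. This stands. A reader might infer that the sponsor means to stop the TLFB at relapse, and the documents do not establish that. They also do not rule it out: item 1 shows that the authors could specify the intervention when they meant it, and item 2 does not.

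The reach is also limited. The item 2 trigger covers relapse during treatment only, in people already at least four weeks free of heavy drinking at entry. The Primary Aim is insomnia severity, and no withdrawal trigger uses the ISI. Later ISI and SF-12 values would be lost with the participant, but a reader should not infer the same outcome-dependent mechanism for Aim 1.

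Finally, a reader might infer that the Aim 2 effect would largely disappear. That would need every relapser to be withdrawn, none to remit, and the whole treatment effect to act through relapse. The documents support none of these.

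**Conclusion.** The passages contradict each other on a point that decides whether the primary alcohol outcome is collected. This is an internal inconsistency that should be fixed. Confidence in the contradiction is high; the harm is conditional. If Section S, item 2 is followed literally and relapse differs by arm, the Aim 2 difference would probably be pulled towards zero. If item 1 governs both arms, there is no such bias. If relapse and its handling are equal across arms, there is about none.

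The documents give no relapse rate, so the size is unknown. The 2.6 to 5.2 points rest on an assumed 10-point difference in withdrawn relapsers, an assumed 95% abstinence without relapse, one reading of the trigger's day count, and no recovery of post-relapse information by the model. They show what is exposed and are not an estimate of bias.

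**What to change.** Reconcile Section S, items 1 and 2 (including the restart text), Section T, items 1.2(f), 1.2(g) and 1.3, and Section V, item 3.3, by separating discontinuation of study therapy from discontinuation of outcome assessment.

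- State that randomized participants in both CBT-I and QDT who stop therapy, or who meet a discontinuation criterion after randomization, remain in scheduled TLFB, ISI and SF-12 assessment through 6 months. The phone and mail routes in Section N, items 2.1.1 and 2.1.2 can be used where needed.
- List the exceptions: withdrawal of consent, a no-contact request, or assessment that is not permitted or not feasible.
- Clarify whether the restart criteria apply to therapy only.
- Optionally, add a sensitivity analysis for days still uncollected after documented relapse.

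The drinking and drug-use thresholds, and the clinical rules for stopping therapy, are for the sponsor to reconcile; none is proposed here.

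Cost: one IRB-approved amendment, possible re-consent (Section V, item 2.1.3), and a few more phone or mail assessments by existing staff.
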